9.5. STUDY MONITORING

Monitoring and auditing procedures approved by the Sponsor will be followed, to comply with GCP guidelines.

The study will be monitored by the Sponsor or its designee. Monitoring will be done by a representative or designee of the Sponsor (site monitor) and will include review of the eCRFs for completeness and clarity, cross-checking with source documents, and clarification of administrative matters. The review of medical records will be performed in a manner to ensure that subject confidentiality is maintained.

The site monitor will ensure that the investigation is conducted per protocol design and regulatory requirements by frequent communications (eg, letter, e-mail, telephone, and fax).

Regulatory authorities, the IRB/IEC, the Institutional Biosafety Committee, and other appropriate institutional regulatory bodies, and/or the Sponsor's clinical quality assurance group may request access to all source documents, eCRFs, and other study documentation for on site audit or inspection. Direct access to these documents must be guaranteed by the Investigator, who must provide support at all times for these activities.

To ensure compliance with GCP and all applicable regulatory requirements, the Sponsor or its designee may conduct a quality assurance audit.

9.6. ETHICS REVIEW

The final study protocol and corresponding ICF must be approved or given a favorable opinion in writing by an IRB or IEC as appropriate. The Investigator must submit written approval to the Sponsor or its designee before he or she can enroll any subject into the study.

The Investigator is responsible for informing the IRB or IEC of any amendment to the protocol in accordance with local requirements. In addition, the IRB or IEC must approve all advertising

used to recruit subjects for the study and any written information to be provided to subjects (eg, drug diaries). The protocol (and corresponding ICF, if applicable) must be re-approved by the IRB or IEC upon receipt of amendments and annually, if local regulations require.

IRB/IEC approval and all materials approved by the IRB for this study must be maintained by the Investigator and made available for inspection.

The PI at each study site is also responsible for providing the IRB with reports of any reportable serious adverse drug reactions from any other study conducted with the investigational product. The Sponsor or its designee will provide this information to the PI.

Progress reports will be provided to the IRB or IEC per local regulations and guidelines.

9.7. DATA HANDLING AND RECORDKEEPING

9.7.1. Case Report Form Completion

The Sponsor or its designee will provide the clinical sites with access to an eCRF for each subject. The Investigator is responsible for ensuring the accuracy, completeness, and timeliness of the data reported in a subject's eCRF. Source documentation supporting the eCRF data should indicate the subject's participation in the study and should document the dates and details of study procedures, AEs, and subject status.

The Investigator or designated representative should complete the eCRF as soon as possible after information is collected. The Investigator must sign and date the eCRF to endorse the recorded data.

9.7.2. Inspection of Records

The Sponsor or its designee will be allowed to conduct site visits to the investigation facilities for monitoring any aspect of the study. The Investigator agrees to allow the monitor to inspect the drug storage area, study drug stocks (if applicable), drug accountability records, subject medical records, other study source documents, and other records relative to study conduct.

9.7.3. Retention of Records

The study Investigator must maintain all documentation relating to the study for a period of 2 years after the last marketing application approval or, if not approved, for 2 years after the discontinuation of the study drug investigational development, or per applicable regulatory requirements.

If the Investigator withdraws from the responsibility of keeping the study records, custody must be transferred to a person willing to accept the responsibility. The Sponsor must be notified in writing if a custodial change occurs.

9.7.4. Publication Policy

All information regarding the study drug is privileged and confidential information. The Investigator agrees to use this information to accomplish the study and will not use it for other purposes without consent from the Sponsor. It is understood that there is an obligation to provide the Sponsor with complete data obtained during the study. The information obtained from the clinical study may be disclosed to regulatory authority(ies), other Investigators, corporate partners, or consultants as required. Study results will be published in accordance with local and national regulations.

The information obtained from the clinical study may be presented at medical congresses or used for scientific exchanges or educational purposes. The information obtained from the clinical study may be disclosed to regulatory authority(ies), other Investigators, corporate partners, or consultants as required.

No publication or disclosure of study results will be permitted except under the terms and conditions of a separate written agreement between the Sponsor and the Investigator and/or the Investigator's institution.

The results of this study will be published in accordance with local regulations and guidance. Authorship eligibility will be determined in accordance with the International Committee of Medical Journal Editors authorship recommendation guidelines.

The Sponsor has full rights over any invention, discovery, or innovation, patentable or not, that may occur when performing the study.

APPENDIX A. WHO 2022 DIAGNOSTIC CRITERIA OF SYSTEMIC MASTOCYTOSIS AND C-FINDINGS

Diagnosis of SM will be based WHO 2022 diagnostic criteria and requires the presence of at least 1 major criterion and at least 1 minor criterion or at least 3 minor criteria.

Major criterion:

Multifocal dense infiltrates of mast cells (≥ 15 mast cells in aggregates) in bone marrow biopsies and/or in sections of other extracutaneous organ(s).

Minor criteria:

- $>25\%$ of all mast cells are atypical cells (type I or type II) on bone marrow smears or are spindle-shaped in dense and diffuse mast cell infiltrates in BM or other extracutaneous organ(s).^a
- Activating *KIT* point mutation(s) at codon 816 or in other critical regions of *KIT*^b in the bone marrow or other extracutaneous organ(s).
- Mast cells in bone marrow, blood, or other extracutaneous organ(s) aberrantly express one or more of the following antigens: CD2, CD25, CD30.^c
- Baseline serum tryptase concentration >20 ng/mL in the absence of a myeloid AHN.^d In the case of a known HAT, the tryptase level should be adjusted.^e

Abbreviations: AHN=associated hematologic neoplasm, HAT=hereditary alpha-tryptasemia, SM=systemic mastocytosis.

^a In tissue sections, an abnormal mast cell morphology counts in both a dense infiltrate and a diffuse mast cell infiltrate. In the bone marrow smear, an atypical morphology of mast cells does not count as an SM criterion when mast cells are located in or adjacent to bone marrow particles. Morphologic criteria of atypical mast cells were referenced in the consensus proposal (Valent et al, 2021).

^b Any type of *KIT* mutation is considered a minor SM criterion when published solid evidence regarding its transforming behavior is available (an overview of potentially activating *KIT* mutations was provided in the supplementary material of Valent et al, 2021).

^c Expression has to be confirmed by either flow cytometry or immunohistochemistry or by both techniques.

^d Myeloid neoplasms can lead to increased serum tryptase levels; thus, this criterion does not count in cases of SM-AHN.

^e A possible method of adjustment has been proposed for known H α T (Valent et al, 2021); the basal tryptase level is divided by 1 plus the extra copy numbers of the alpha tryptase gene. For example, when the tryptase level is 30 and 1 extra copy of the alpha tryptase gene is found, the H α T-corrected tryptase level is 15 ($30/2 = 15$), and therefore, it is not a minor SM criterion in this case.

Adapted from El Hussein et al, 2022.

C-Findings:

C-Findings are indicative of organ damage produced by mast cell infiltration (should be confirmed by biopsy if possible).

1. Bone marrow dysfunction caused by neoplastic mast cell infiltration manifested by ≥ 1 cytopenia: absolute neutrophil count $<1.0 \times 10^9/L$, hemoglobin level <10 g/dL, and/or platelet count $<100 \times 10^9/L$
2. Palpable hepatomegaly with impairment of liver function, ascites, and/or portal hypertension

3. Skeletal involvement, with large osteolytic lesions (if the size of the lesion is ≥ 2 cm, it is considered large) with or without pathological fractures (pathological fractures caused by osteoporosis do not qualify as a C-finding). Small osteolytic and/or sclerotic lesions do not define advanced SM
4. Palpable splenomegaly with hypersplenism (defined as platelet count $< 100,000$ due to sequestration from the large spleen)
5. Malabsorption with weight loss due to gastrointestinal mast cell infiltrates (recommended to be in combination with 1 additional C-finding for eligibility)

APPENDIX B. 2016 WHO SYSTEMIC MASTOCYTOSIS VARIANTS

ISM

1. Meets the general criteria for SM
2. No C-findings
3. No evidence of an AHN
4. Low mast cell burden
5. Skin lesions are often present

Bone Marrow Mastocytosis

1. As above for ISM, but with BM involvement and no skin lesions

Smoldering SM

1. Meets the general criteria for SM
2. ≥ 2 B-findings; no C-findings
3. No evidence of an AHN
4. Does not meet criteria for MCL

SM-AHN[‡]

1. Meets the general criteria for SM
2. Meets the criteria for an AHN (ie, a myelodysplastic syndrome, myeloproliferative neoplasm, acute myeloid leukemia, lymphoma, or another hematologic neoplasm classified as a distinct entity in the WHO classification)

ASM[§]

1. Meets the general criteria for SM
2. ≥ 1 C-finding
3. Does not meet criteria for MCL
4. Skin lesions are usually absent

MCL[¥]

1. BM aspirate smears show $\geq 20\%$ mast cells
2. In classic cases, mast cells account for $\geq 10\%$ of the peripheral blood WBCs, but the aleukemic variant (in which mast cells account for $< 10\%$) is more common
3. Mast cell variants include:
 - a. Acute MCL [≥ 1 C-finding(s)] vs. chronic MCL (no C-findings)
 - b. MCL with an AHN vs MCL without and AHN
 - c. Primary (de novo) vs secondary MCL (arising from another SM variant)
4. Skin lesions are usually absent

Abbreviations: AHN=associated hematologic neoplasm, ASM=aggressive systemic mastocytosis, BM=bone marrow, ISM=indolent systemic mastocytosis, MCL=mast cell leukemia, MDS=myelodysplastic syndromes, MPN=myeloproliferative neoplasms, SM=systemic mastocytosis, SM-AHN=SM with an associated hematologic neoplasm, WBC=white blood cell, WHO=World Health Organization.

‡ Usually, a myeloid neoplasm (ie, MDS, MPN, MDS/MPN, chronic eosinophilic leukemia, not otherwise specified, or acute myeloid leukemia). Lymphoid neoplasms (ie, multiple myeloma and chronic lymphocytic leukemia) constitute <10% of associated hematologic neoplasms.

§ ASM with 5% to 19% mast cells in BM aspirate smears is referred to as ASM in transformation and reflects evolution toward MCL.

¥ The aleukemic MCL variant (in which mast cells account for <10% of circulating white blood cells) is more common than cases with $\geq 10\%$ circulating mast cells, which are more aggressive; MCL has also been divided into chronic (C-findings absent) and acute (C-findings present).

Adapted from [Gotlib et al, 2013](#).

APPENDIX C. MEASURABLE C-FINDINGS PER MODIFIED IWG-ERT-ECNM

Measurable C-findings (ie, organ damage) allowed for eligibility (per modified IWG-MRT-ECNM consensus response criteria: eligibility and response criteria for CI):

	mIWG-MRT-ECNM Organ Damage Eligible for CI Response	mIWG-MRT-ECNM CI Response Criteria
Ascites or pleural effusions	
 Symptomatic ascites or pleural effusion requiring medical intervention such as: Use of diuretics (Grade 2) OR ≥ 2 therapeutic paracenteses or thoracenteses (Grade 3) at least 28 days apart over 12 weeks before the start of treatment with one procedure performed 6 weeks before the start of treatment 	
 Complete resolution of symptomatic ascites or pleural effusion (including trace or minimal on radiographic imaging)* AND No longer in need of diuretic(s) for ≥ 12 weeks OR No therapeutic paracenteses or thoracentesis for ≥ 12 weeks
Liver function abnormalities	
\geq Grade 2 abnormalities in direct bilirubin ($>1.5 \times \text{ULN}$), AST ($>3.0 \times \text{ULN}$), ALT ($>3.0 \times \text{ULN}$), or ALP ($>2.5 \times \text{ULN}$) in the presence of:
 
 Ascites and/or Clinically relevant portal hypertension, and/or Liver MC infiltration that is biopsy-proven or Other causes for abnormal liver function are not identified 	Reversion of ≥ 1 LFTs to normal range for ≥ 12 weeks
Hypoalbuminemia	\geq Grade 2 hypoalbuminemia (<3.0 g/dL)	Reversion of albumin to normal range for ≥ 12 weeks
Marked splenomegaly	Symptomatic or non-symptomatic spleen that is palpable >5 cm below the left costal margin and patient endorses symptoms of discomfort and/or early satiety	$\geq 35\%$ reduction in spleen volume based on 3D MRI or CT scan (when available), or else $\geq 50\%$ reduction in palpable splenomegaly, for ≥ 12 weeks
Neutropenia	\geq Grade 3 ANC ($<1.0 \times 10^9/\text{L}$)	$\geq 100\%$ increase in the ANC and an absolute increase $\geq 0.5 \times 10^9/\text{L}$ for ≥ 12 weeks (with allowance for CRh)
Anemia (transfusion-independent)	\geq Grade 2 Hgb (<10 g/dL)	An increase in Hgb of ≥ 2 g/dL that is maintained for ≥ 12 weeks (with allowance for CRh)
Anemia (transfusion-dependent)	Transfusion of ≥ 6 units PRBCs in the 12 weeks before the start of treatment with the most recent transfusion occurring within the 4 weeks before the start of	Transfusion independence for ≥ 12 weeks and maintenance of Hgb ≥ 8.5 g/dL at the end of the 12-week

	mIWG-MRT-ECNM Organ Damage Eligible for CI Response	mIWG-MRT-ECNM CI Response Criteria
	treatment and RBC transfusions are only considered as part of the baseline criteria if they are administered for Hgb ≤ 8.5 g/dL and are not associated with bleeding, hemolysis, or therapy	period of response duration (with allowance for CRh)
Thrombocytopenia (transfusion-independent)	\geq Grade 2 thrombocytopenia ($<75 \times 10^9/L$)	$\geq 100\%$ increase in the platelet count and an absolute platelet count increase of $\geq 50 \times 10^9/L$ and no need for platelet transfusion for ≥ 12 weeks (with allowance for CRh)
Thrombocytopenia (transfusion-dependent)	
 1. Transfusion of ≥ 6 units of apheresed platelets during the 12 weeks preceding treatment AND 2. ≥ 2 units transfused in the previous 4 weeks AND 3. Transfusions administered only for a platelet count $< 20 \times 10^9/L$ 	Transfusion-independence for ≥ 12 weeks and maintenance of platelet count $\geq 20 \times 10^9/L$ (with allowance for CRh)

Abbreviations: ALP=alkaline phosphatase, ALT=alanine aminotransferase, ANC=absolute neutrophil count, AST=aspartate aminotransferase, BM=bone marrow, CI=clinical improvement, CRh=complete recovery with incomplete hematologic recovery, CT=computed tomography, Hgb=hemoglobin, IWG-MRT-ECNM=International Working Group-Myeloproliferative Neoplasms Research and Treatment European Competence Network on Mastocytosis, LFT=liver function test, MC=mast cell, mIWG-MRT-ECNM=modified International Working Group- Myeloproliferative Neoplasms Research and Treatment European Competence Network on Mastocytosis, MRI=magnetic resonance imaging, PRBC=packed red blood cell, RBC=red blood cell, ULN=upper limit of normal.

CRh (CR with partial hematologic recovery) requires the following minimum levels for peripheral blood counts: absolute neutrophil count $\geq 0.5 \times 10^9/L$ with normal differential (absence of neoplastic mast cells and blasts $< 1\%$) and platelet count $\geq 50 \times 10^9/L$ and hemoglobin ≥ 8.0 g/dL.

*Radiologic use of the term “trace” or “minimal” for ascites or pleural effusion indicates a substantial improvement of pretreatment pathologic fluid accumulation, which required medical intervention. These terms are acceptable in the absence of the radiologists’ use of the term(s) “complete disappearance” or “resolution” to describe the change in ascites or effusion.

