APPENDIX D. MODIFIED (M)IWG-ERT-ECNM CRITERIA FOR OVERALL RESPONSES IN PATIENTS WITH ADVSM

Response Assessment	mIWG-MRT-ECNM Response Criteria
Complete remission (CR)*	
Requires all 4 of the following criteria and response duration must be ≥ 12 weeks:
 
No presence of compact neoplastic mast cell aggregates in the BM or other biopsied extracutaneous organ
 
Serum tryptase level < 20 ng/mL[†]
 
Peripheral blood count remission defined as: ANC $\geq 1 \times 10^9$/L with normal differential (absence of neoplastic mast cells and blasts $< 1\%$) and Platelet count $\geq 100 \times 10^9$/L and Hgb level ≥ 11 g/dL
 
Complete resolution of palpable hepatosplenomegaly and all biopsy-proven or suspected SM-related organ damage (C-findings)[‡]

CR with partial recovery of peripheral blood counts (CRh)*
 
Requires all criteria for CR be met and response duration must be ≥ 12 weeks; however, patient may have residual cytopenias.
	
Requires all criteria for CR be met and response duration must be ≥ 12 weeks; however, patient may have residual cytopenias. The following minimum recovery of peripheral blood counts is required:
 
ANC $> 0.5 \times 10^9$/L with normal differential (absence of neoplastic mast cells and blasts $< 1\%$) and Platelet count $> 50 \times 10^9$/L and Hgb level > 8.0 g/dL

Partial Remission (PR)*	
Requires all 3 of the following criteria, and response duration must be ≥ 12 weeks, in the absence of both CR and PD:
 
Reduction by $\geq 50\%$ in neoplastic mast cells in the BM and/or other extracutaneous organ at biopsy demonstrating eligible SM-related organ damage
 
Reduction of serum tryptase level by $\geq 50\%$[†]
 
Resolution of ≥ 1 biopsy-proven or suspected SM-related organ damage (C-finding[s])[‡]

Clinical Improvement (CI)*	
Response duration must be ≥ 12 weeks
 
Requires ≥ 1 of the nonhematologic and/or hematologic response criteria to be fulfilled in the absence of CR, CRh, PR, or PD

Stable disease (SD)	Not meeting criteria for CR, CRh, PR, CI, or PD
Progressive Disease (PD) [§]	Requires at least 1 element from the criteria below; duration must be ≥ 4 weeks:

Response Assessment **mIWG-MRT-ECNM Response Criteria**

	Baseline	Post-Baseline
	Any grade 2 non-hematologic organ damage	Worsening by 1 grade and minimum 100% increase (doubling) of laboratory abnormality
	≥Grade 2 albumin	Worsening by 1 grade and decrease by ≥0.5 g/dL

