- § Preservation of at least 1 CI finding permits a patient to maintain the response of CI if 1 or more CI findings are lost but none meet criteria for PD. However, if 1 or more of the CI findings become PD, then the CI finding assignment is lost and the patient meets criteria for PD. The baseline value for evaluating PD is the pretreatment measurement(s). The PD findings must be considered related to the underlying disease and not to other clinical factors. Progression of an underlying chronic myeloid neoplasm to acute myeloid leukemia is also considered PD.

Adapted from [NCCN Systemic Mastocytosis, Version 3.2021](#).

APPENDIX E. COMPARISON OF IWG-MRT-ECNM AND MODIFIED (M)IWG-MRT-ECNM RESPONSE CRITERIA FOR CLINICAL IMPROVEMENT (CI)

	IWG-MRT-ECNM Definition	IWG-MRT-ECNM Response Criteria	mIWG-MRT-ECNM Modifications
Non-hematologic C-Findings			
Ascites or pleural effusions	Symptomatic ascites or pleural effusion requiring medical intervention such as: Use of diuretics (grade 2) or ≥2 therapeutic paracenteses or thoracenteses (grade 3) at least 28 days apart over 12 weeks before the start of treatment with one procedure performed 6 weeks before the start of treatment	Complete resolution of symptomatic ascites or pleural effusion (including trace or minimal on radiographic imaging) and no longer in need of diuretics for ≥12 weeks and No longer in need of diuretics for ≥12 weeks or No therapeutic paracenteses or thoracentesis for ≥12 weeks	As IWG-MRT-ECNM
Liver function abnormalities	≥Grade 2 abnormalities in direct bilirubin ($>1.5 \times \text{ULN}$), AST ($>3.0 \times \text{ULN}$), ALT ($>3.0 \times \text{ULN}$), or ALP ($>2.5 \times \text{ULN}$) in the presence of: Ascites and/or Clinically relevant portal hypertension, and/or Liver MC infiltration that is biopsy-proven or No other identified cause of abnormal liver function	Reversion of ≥1 LFTs to normal range for ≥12 weeks	As IWG-MRT-ECNM
Hypoalbuminemia	≥Grade 2 hypoalbuminemia ($<3.0 \text{ g/dL}$)	Reversion of albumin to normal range for ≥12 weeks	As IWG-MRT-ECNM

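### The ascites/effusion rule for Clinical Improvement is not tied to the entry route, and Appendices C and E can classify the same diuretic-treated subject oppositely

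*Protocol*

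**What the plan says.** **Entry.** Inclusion criterion 2 (Protocol Section 4.1) sends the reader to Appendix C for measurable disease. The ascites/effusion row there requires "Symptomatic ascites or pleural effusion requiring medical intervention such as", with two alternatives: "Use of diuretics (Grade 2) OR" at least two therapeutic paracenteses or thoracenteses (Grade 3) before treatment.

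**Response, Appendix C.** Three conditions are listed in this order:
- "Complete resolution of symptomatic ascites or pleural effusion", with trace or minimal fluid on imaging accepted, followed by AND;
- "No longer in need of diuretic(s) for" at least 12 weeks, followed by OR;
- "No therapeutic paracenteses or thoracentesis for" at least 12 weeks.

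There are no brackets, and nothing says which limb applies to which entry route.

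**Response, Appendix E.** The comparison table words the first condition differently: "including trace or minimal on radiographic imaging) and no longer in need of diuretics for" at least 12 weeks. It then repeats the diuretic condition after an *and*, and adds the procedure condition after an *or*. The column for modifications marks this row as the same as the unmodified consensus criterion.

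**Consequence for the endpoint.** Appendix D needs only one of the "nonhematologic and/or hematologic response criteria to be fulfilled in the absence of CR, CRh, PR, or PD", held for at least 12 weeks. Section 8.7 counts CI with CR, CRh and PR as a confirmed response in the primary ORR, as assessed by the Central Response Review Committee (CRRC).

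**The concern.** A response criterion should require a change in the finding that qualified the subject. Here a subject can enter because the fluid needs diuretics and be classed as improved while still on them, because the condition that completes the rule concerns a procedure the subject never had. That condition is true before the first dose, so the 12-week requirement adds nothing to that limb.

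The protocol handles comparable findings more carefully. Anemia and thrombocytopenia each have separate transfusion-independent and transfusion-dependent rows in Appendix C, each with its own response rule. Ascites/effusion merges two routes defined by intervention into one row and lets the condition for one route satisfy the response for the other.

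Part 2 Stage 2 is uncontrolled and its ORR is tested against a fixed 28%. Any subject classed as a responder by an unintended reading therefore adds directly to the estimate and the test. Because the two appendices word the rule differently, the classification also depends on which one the CRRC applies.

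**Working it through.** **Inputs.** Appendix C and Appendix E (ascites/effusion rows), Appendix D (one CI criterion suffices), Section 8.7 (CI is a response; test against 0.28, one-sided 0.025), Section 8.2 (55 evaluable subjects).

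**Step 1: truth table.** Let A = fluid resolved, B = off diuretics for at least 12 weeks, C = no procedure for at least 12 weeks. Take a diuretic-qualified subject with no procedures who stays on diuretics, so B = 0 and C = 1.

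| Rule | Resolved (A = 1) | Not resolved (A = 0) |
|---|---|---|
| Appendix C as A AND (B OR C) | responder | non-responder |
| Appendix C as (A AND B) OR C | responder | responder |
| Appendix E as A AND B AND (B OR C) | non-responder | non-responder |
| Appendix E as (A AND B) OR C | responder | responder |
| Matched to entry route: A AND B | non-responder | non-responder |

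In the resolved column, both groupings of Appendix C give a responder. This result therefore does not depend on brackets, or on list indentation that may have been lost in the text at hand. Under its natural grouping Appendix E gives the opposite answer. The unresolved column matters only if the procedure limb is allowed to stand alone.

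**Step 2: can the effect on ORR be sized?** It needs the share *f* of subjects whose only route to response is this finding, and the protocol does not give it. The planned sample size and power do not depend on the grouping. What follows is a worst-case illustration only, with *f* assumed and every affected subject counted as a responder, which requires the (A AND B) OR C grouping.

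Rejection threshold at n = 55:
- z = (22/55 − 0.28) / √(0.28 × 0.72 / 55) = 1.98, above 1.96. At 21/55, z = 1.68.
- So the uncorrected test rejects from 22/55. With a continuity correction it rejects from 23/55.

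Apparent rate if the true rate is 28%: p = 0.28 + 0.72 × *f*. Exact binomial tails:

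| Assumed *f* | p | P(X ≥ 22) | P(X ≥ 23) |
|---|---|---|---|
| 0 | 28.0% | 3.7% | 1.9% |
| 3% | 30.2% | 7.7% | 4.4% |
| 5% | 31.6% | 11.7% | 7.1% |
| 10% | 35.2% | 27.0% | 18.7% |

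The 3.7% at *f* = 0 already exceeds 2.5%. That comes from the chi-square approximation and has nothing to do with this criterion.

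Under A AND (B OR C) a subject must still resolve, so the effect is smaller. If, as a further assumption, half of the affected subjects who would otherwise be non-responders resolve on continued diuretics, then p = 0.28 + 0.36 × *f*. P(X ≥ 22) is then 6.9% at *f* = 5% and 11.7% at *f* = 10%.

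**The case against.** A reader might infer that unchanged, diuretic-treated ascites counts as a response, so that every diuretic-qualified subject responds without any drug effect. The documents do not support that as the intended meaning. It needs the procedure limb to stand alone, and the layout of Appendix C points the other way. Resolution comes first, followed by AND, and the two alternatives after it mirror the two entry routes. The footnote on how radiology terms satisfy resolution would be idle for anyone passing on the procedure limb. Entry requires symptomatic fluid, so under the natural grouping the response is not met on Day 1. The text does not exclude the looser grouping, but the false-positive figures rest on it and on assumed shares. Appendix C lists nine kinds of finding, and nothing indicates that as many as 10% of subjects would have only this one.

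Two further defences carry some weight. The row is marked as following the published consensus criteria, so it is not presented as a loosening made for this trial. And responses are adjudicated by the CRRC, which includes independent members and mastocytosis specialists and may have a charter that settles the matter. Neither cures the text: the committee is asked to apply these criteria, and the two appendices give it different ones.

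It is also fair that a diuretic-qualified subject may have had a single procedure before treatment. The procedure limb is met at baseline only by those with none in the preceding 12 weeks.

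What stands is the resolved-on-diuretics case and the disagreement between Appendices C and E.

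**Conclusion.** The point holds in this form. Under Appendix C, a diuretic-qualified subject with no procedures whose fluid resolves while diuretics continue is CI on either grouping, and so a responder in the primary ORR. Under the natural grouping of Appendix E the same subject is a non-responder, although Appendix E presents the criterion as unmodified. This is a defect in a stated primary-endpoint rule.

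Its size cannot be derived from the protocol. It depends on how many subjects have diuretic-treated fluid as their only route to response, and on how many of them resolve without stopping diuretics. The 7.7% to 27% range (rejection at 22/55) is a worst case that adds the looser grouping and assumed shares of 3% to 10%; it is not an estimate. The risk runs towards an inflated ORR and type I error. Power is not the issue: rejecting at 22/55, the exact power at a true ORR of 60% is 99.9%.

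**What to change.** Before the CRRC adjudicates Stage 2, replace the ascites/effusion rows of Appendices C and E with one identical, explicitly grouped rule and carry it into the CRRC charter:
- complete resolution, as footnoted in Appendix C, is required in all cases; **and**
- for subjects who qualified on diuretics, the diuretic limb must be met for at least 12 weeks;
- for subjects who qualified on procedures, the procedure limb must be met for at least 12 weeks.

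The rule should also say what applies to a subject who met both entry alternatives. No condition beyond those already in the two appendices is needed. A further requirement that no diuretic be newly started or increased appears in neither and should not be added under this point. The change concerns endpoint classification only and leaves the use of diuretics or drainage in patient care untouched.

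The cost is the wording of two table rows and a charter entry. Medications are already collected through 30 days after the last dose (Section 6.16.2). Section 6.4 covers procedures before entry; the team should confirm that the eCRF also captures paracentesis and thoracentesis on study. A few subjects may move from CI to stable disease.
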